2.1.5 The role of medical thoracoscopy in pleural infection

In a few isolated centres on the European continent, the use of medical thoracoscopy for pleural infection is relatively common. However, there are currently only four published studies relating to this

practice: None of them are comparative or randomised; describe UK patients; include patient-subjective outcomes; look at rapidity of performing the procedure or duration of stay; or include flexible thoracoscopy. (28-31) A total of 191 patients are reported overall, the bulk coming from a paper by Brutsche et al, who undertook a multicentre retrospective review series of patients from three hospitals in Italy and Switzerland over a 14-year period. A third of this series' cases were performed as a result of failed initial tube drainage and half received post-procedure intrapleural fibrinolytics (albeit without DNase).

Despite their limitations, however, these studies would seem to support the hypothesis that medical thoracoscopy can be performed safely in this population, with complication rates akin to those seen in other thoracoscopy studies. Clinical outcomes were also encouraging, with a combined rate of 90% (172/191) of patients for avoiding surgery.

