2.2 RATIONALE FOR CURRENT STUDY

2.2.1 The need for the SPIRIT trial

At the time of writing, UK thoracoscopy services are largely geared towards elective diagnostic procedures, with those who do undertake LAT for therapeutic purposes tending to do so only in the malignant population. In this group, the primary perceived benefit of choosing LAT over standard chest drain insertion is the ability to completely drain the pleural cavity and administer talc in a single procedure. Although logistically more challenging and slightly more demanding for patients, this approach is typically able to reduce the number of days spent in hospital such that there is likely to be a significant healthcare cost benefit. Given that patients with pleural infection can have average inpatient stays in excess of those with malignancy, the question of whether a similar reduction can be achieved by using LAT in this population is an important one. If either this, or an improvement in the need for step-up treatment, can be demonstrated then it could be argued that therapeutic medical thoracoscopy would represent a new standard of care for pleural infection in the UK, necessitating a shift in long-term service provision.

The most appropriate way to address the above is with a randomised controlled trial comparing the newer intervention to the current standard. However, before this can be attempted, it must be shown that there is enough flexibility in current set-ups to allow for urgent or semi-urgent thoracoscopy to be performed, as patients cannot be left with untreated pleural infection for extended periods of time. The SPIRIT trial will address this question directly, examining the feasibility of randomising patients to undergo either standard care or rapid medical thoracoscopy. This, along with the collection of basic

outcome and patient experience data, will hopefully allow the design and justification of a larger trial which is fully powered to evaluate those outcomes on a larger scale.

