3.2 SECONDARY RESEARCH QUESTIONS

Regarding those patients who are treated with medical thoracoscopy for pleural infection:

1. Does this approach reduce the time spent in hospital compared to standard treatment?
2. Does this approach affect the need for “step-up” therapy?
3. Does this approach affect lung function over the weeks following treatment?
4. Does this approach affect pleural effusion size or overall complexity, measured radiologically over time?
5. Does this approach affect the microbiological yield in comparison to standard sampling techniques?
6. How does using this approach affect overall costs compared to standard treatment?
7. How does using this approach affect patients’ subjective quality of life?
8. What are patients’ experiences of trial involvement and of the procedures themselves?

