4.3.2 Secondary outcomes

- Duration of stay due to pleural infection, as measured by the number of nights in hospital between enrolment and being recorded as medically fit for discharge
- Total inpatient time, as measured by the number of nights in hospital between enrolment and the end of the 90-day post-procedure follow-up period
- Need for step-up therapy, as measured by the difference in proportion of patients requiring intrapleural fibrinolytic therapy or referral for surgical debridement
- All-cause mortality, as measured by the number of patients remaining alive at days 30 and 90 post procedure
- Degree of pleural fluid septation, as measured by the change in bedside thoracic ultrasound septation score from baseline to follow-up days 1, 3, 7, 30 and 90 post procedure
- Pleural effusion size, as measured by the change in radiographic hemithorax opacification from enrolment to discharge, and days 1, 30 and 90 post procedure
- Microbiological yield, as measured by the difference in proportion with positive culture or stain between the control and intervention arms
- Total costs of interventions, as measured by the difference in total cost of treatment for pleural infection (from enrolment to being medically fit for discharge) between two arms
- Quality of life, as measured by the change in EQ-5D subjective health score from baseline to days 30 and 90 post procedure
- Patient experiences, as determined by exploring patients' perceptions and experiences of interventions before and after their procedure through semi-structured interviews

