4.5 TRIAL DESIGN JUSTIFICATION

- As mentioned above, the role of medical thoracoscopy in the management of pleural infection is largely unexplored. Theoretically, this intervention may have a place at any stage, ranging from first fluid drainage through to using it as a tool to try to avoid surgery in those who have failed first-line drainage, or even as an alternative to more invasive VATS procedures in those with persistent non-resolving disease. This study has chosen to focus on the former, and examines whether using medical thoracoscopy as the first intervention in pleural infection is feasible and acceptable. The primary rationale for this is minimising the demand for UK thoracoscopists to undertake procedures outside of their typical experience, which lies in the management of collections which should theoretically respond to standard drainage.
- SPIRIT is a feasibility study as opposed to a pilot study, which means the information it is able to generate will hopefully be used to *inform the design* of a larger study examining the efficacy of LAT in the pleural effusion population, rather than being a smaller but fixed template for such a study.
- The decision to target a relatively selected pleural infection cohort for randomisation has been carefully considered. It would be possible to design the SPIRIT trial to include and randomise all pleural infection patients needing drainage regardless of day or time of presentation, or indeed of 'suitability' for LAT, and then analyse them on an intention-to-treat basis to determine the 'real-world' impact of using LAT in this population. This approach would theoretically minimise selection bias. However, given that very few (if any) UK centres are currently set up to perform urgent thoracoscopy, and not all investigators would be comfortable performing LAT in a completely unselected population, this approach would likely place investigators in the situation of having to consent patients to potentially being randomised to a treatment arm they know they will not be able to deliver. Aside from the ethical issues this may raise, it would likely also lead to a significant number of allocation failures in the LAT arm and would thus blunt the ability to interpret any data based on comparisons with this group.

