6.3.3 Allocation failures

The nature of a participant's care is at all times the responsibility of the treating physician. However, on any occasion where treatment differs from that specified in the trial protocol then a protocol deviation form should be completed. In addition, patients who do not undergo their allocated procedure will be recorded as "allocation failures." The full reasons for all allocation failures should be recorded.

In the control arm, an allocation failure will refer to any patient who does not have a chest drain performed within the stipulated time window, or does not have a chest drain insertion performed as allocated.

In the intervention arm, an allocation failure will refer to any patient who does not have a medical thoracoscopy within the stipulated time window. Such patients should, in the first instance, aim to have a 16F gauge (or larger) chest drain performed as per the control arm.

If a patient is unable to undergo their allocated procedure, all subsequent tests and follow-up visits should be timed from the day of randomisation.

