6.3.5 Use of intrapleural enzyme therapy

Intrapleural enzyme therapy, such as tPA and DNase, may be used in trial participants (in either treatment arm) at the discretion of the treating physician. As a guideline, however, the use of these agents should follow standard practice and be reserved for those who are continuing to demonstrate evidence of active pleural infection despite intercostal drainage. In all trial patients, the use of enzyme therapy should be considered in the following circumstances:

- Persistent or rising inflammatory markers on the second day post trial procedure
- Persistent or intermittent fevers on the second day post procedure

- Radiological evidence of ongoing fluid collection with no associated fluid output on the second day post procedure

The need for intrapleural enzyme therapy will be recorded as a trial outcome measure.

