9.7 CONSENT

Consent to trial participation must be sought from each potential participant only after a full explanation has been given and a patient information sheet offered. Due to the relatively acute nature of pleural infection, whereby those requiring chest drainage would normally be expected to undergo their procedure as soon as possible, as well as the likely difficulties which will be associated with having to arrange an urgent medical thoracoscopy in some patients, it is not felt practical to mandate participants have 24 hours or more to consider trial entry. However, it is imperative that all participants be given sufficient time (as determined by the participant themselves) for trial information to be considered and for questions to be asked. Signed participant consent should ideally be obtained, but for those patients who are unable to provide a signature an alternative identifying mark (such as a fingerprint) may be used if witnessed by a third party signatory. The right of the participant to refuse to participate without giving reasons must be respected.

In addition to consent for the study, separate written consent should be taken for the allocated trial intervention in accordance with the recruitment centre's local guidance. For those patients who are approached to have a semi-structured interview, a verbal confirmation of consent should be sought at

the time of questioning. Written consent should also be obtained for any additional party who contributes to the semi-structured interview.

After the participant has entered the study, the treating clinician remains free to give alternative treatment to that specified in the protocol at any stage if he/she feels it is in the participant's best interest, but the reasons for doing so should be recorded. In these cases the participants remain within the study for the purposes of follow-up and data analysis. All participants are free to withdraw at any time from the protocol treatment without giving reasons and without prejudicing further treatment.

If a trial participant loses the capacity to consent during the trial then they will be withdrawn from the trial at that point. Data collected with their consent up until the point they lose capacity may be used.

Details of consent relating to the semi-structured interview component of the trial is covered in Appendix 4 (section A4.7).

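### The step-up outcome omits thoracoscopy given after a failed control drain, so that escalation is scored as no step-up

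*Protocol*

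**What the plan says.** Secondary research question 2 (Protocol 3.2) asks: "Does this approach affect the need for “step-up” therapy". Section 4.3.2 turns this into "Need for step-up therapy, as measured by the difference in proportion of patients requiring intrapleural fibrinolytic therapy or referral for surgical debridement". Section 6.3.5 supports the first component: "The need for intrapleural enzyme therapy will be recorded as a trial outcome measure". Section 6.3.6 says the same of surgical referral. No section names a later thoracoscopy, or any other repeat pleural procedure, as a step-up event or as another outcome.

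Three other places bear on the point.

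- Section 9.7 says that after entry "the treating clinician remains free to give alternative treatment to that specified in the protocol at any stage". The reasons are to be recorded, and the patient stays in follow-up and analysis.
- Section 4.5 lists possible roles for thoracoscopy, "ranging from first fluid drainage through to using it as a tool to try to avoid surgery in those who have failed first-line drainage". It then states that this study looks at first-line use.
- Section 6.3.3 makes a control patient an allocation failure if the drain is not placed within the time window, or if the patient "does not have a chest drain insertion performed as allocated". It also asks for a deviation form whenever treatment departs from the protocol.

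**The concern.** The outcome is meant to show how often the first procedure was not enough. Two kinds of further treatment are counted. A third kind, the trial's own experimental procedure given after a drain has failed, is possible under section 9.7 and is not counted. Used in that way it may take the place of an enzyme course or a surgical referral that would have counted.

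The gap is not even between the arms. Intervention patients have normally had their thoracoscopy already, so a first thoracoscopy as rescue can arise essentially only in the control arm, apart from intervention patients whose allocated procedure was not delivered. Each case removes a control failure from the count and makes the control drain look better than it was. The trial is open label (6.2.3), so clinicians know which patients have not had the procedure.

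At stake is the answer to secondary question 2, and the step-up rates that the designers of a larger trial would take from this one.

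**Working it through.** **1. The plan's own figure.** Section 7.1.1 expects about 150 patients a year and recruitment of one in five: 150 × 1/5 = 30, which reproduces the stated sample size. Section 4.2 allocates 1:1, so 30/2 = 15 per arm. There is no power calculation to reproduce.

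**2. One patient traced through the rules.** Take a control patient who is drained within the window, whose infection persists, and who then has a thoracoscopy without enzymes or a surgical referral.

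| Rule | Result for this patient |
|---|---|
| Allocation failure (6.3.3) | No: the allocated drain was placed in time |
| Step-up (4.3.2) | No: neither component occurred |
| In the intention-to-treat analysis (7.1.3, 9.7) | Yes, as a control patient without step-up |
| Deviation form or recorded reason (6.3.3, 9.7) | Yes, but it feeds no outcome |
| Stay and treatment cost (4.3.2) | Affected indirectly; the rescue itself is not counted |

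A per-protocol analysis might leave the patient out, but it would not count the escalation either.

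**3. Size per patient.** If e control patients truly need escalation and k of them are rescued by thoracoscopy alone, the recorded control proportion is (e − k)/15. The shift is k/15:

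- k = 1: 1/15 = 6.7 points
- k = 2: 2/15 = 13.3 points
- k = 3: 3/15 = 20.0 points

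**4. Illustration (assumed counts, not in the documents).** Suppose 6/15 control and 3/15 intervention patients truly need escalation.

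| k unscored | Control | Intervention | Difference | Fisher p |
|---|---|---|---|---|
| 0 | 6/15 | 3/15 | 20.0 points | 0.43 |
| 1 | 5/15 | 3/15 | 13.3 points | 0.68 |
| 2 | 4/15 | 3/15 | 6.7 points | 1.0 |
| 3 | 3/15 | 3/15 | 0 points | 1.0 |

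Sampling error is large even with nothing missed. For 6/15 against 3/15 the standard error is √(0.4 × 0.6/15 + 0.2 × 0.8/15) = √0.02667 = 0.163. The Wald 95% interval is 0.20 ± 1.96 × 0.163, or about −12 to +52 points.

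**The case against.** The strongest reply is that the outcome fits the pathway the protocol describes. Sections 2.1.3, 6.3.5 and 6.3.6 run from drain to enzymes to surgery, and the outcome counts exactly those two escalations. Section 4.5 treats rescue thoracoscopy as a theoretical use and chooses first-line use instead. It adds that hardly any UK centre is set up for urgent thoracoscopy. The patient at issue must also receive neither enzymes nor a referral, although section 6.3.5 asks that enzymes be considered in every patient with signs of persisting infection on the second day. All of this stands as a reason to expect few such patients. It does not change how one is scored.

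Four stronger readings are tempting, and the documents do not support them.

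- *Step-up decides whether a larger trial goes ahead.* Section 2.2.1 says "If either this, or an improvement in the need for step-up treatment, can be demonstrated", but the consequence it draws is a possible new standard of care. The success criteria in section 7.1.2 concern feasibility only.
- *Rescue thoracoscopy is readily available to controls.* Inclusion criterion 2 concerns the same or next day after drainage is judged necessary, not capacity days later. Section 2.1.5 does report that "A third of this series' cases were performed as a result of failed initial tube drainage", but that is a retrospective series from Italy and Switzerland, and half of its patients also received fibrinolytics afterwards.
- *Uncounted second drains are equally one-sided.* Both arms end their procedure with a drain (6.3.1, 6.3.2), so second drains can occur in either.
- *Crossover goes unrecorded.* Deviation forms and recorded reasons would capture much of it. What is missing is its place in the outcome.

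**Conclusion.** The point holds in a limited form. As written, the step-up measure scores a control patient escalated to thoracoscopy alone as needing no step-up, and this omission can run essentially only against the thoracoscopy arm. Each such patient moves the control proportion by 6.7 percentage points, assuming exactly 15 per arm. The total effect cannot be stated, because the documents give no rescue rate. It could be nil, and the fall from 20 points to 0 shown above depends wholly on assumed counts.

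The primary feasibility criteria do not change. With no formal power and intervals this wide, no firm conclusion on step-up would be drawn in either case. The harm is to an estimate meant to inform later design, and the remedy is cheap enough to justify the change.

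**What to change.** In section 4.3.2, add a third component to step-up: medical thoracoscopy performed after the initial drain for persisting pleural infection, counted alongside enzyme therapy and surgical referral. Report each component and the number of crossovers by arm. Keep the current two-part measure as a sensitivity analysis, so that nothing is lost.

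Report further drains or aspirations for persisting infected fluid separately by arm and outside the composite, since they can occur in either arm and are more discretionary in an open-label trial. Keep them distinct from replacement of a drain that was dislodged or blocked, which section 8.3 lists as expected.

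This changes only what is counted, not any treatment decision. The cost is a few lines of outcome wording, one extra eCRF field and a slightly broader composite, which the component table makes transparent.

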6.2.3 Blinding

The SPIRIT trial will be conducted on an “open label” basis. As such, treatment allocation will not be concealed from either participants or trial personnel. No attempt at “sham” procedures will be made.

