6.5 IMAGING

6.5.1 Thoracic ultrasound

All thoracic ultrasound scans are to be performed as part of standard clinical care. Scan results should be documented during the baseline assessment; on the first, third and seventh days post allocated procedure (and then every seven days (+/- 1 day) after that if the patient remains in hospital); and at the time of the day 30 and day 90 follow-up appointments. The scans on days one and three do not need to be completed if they fall outside of normal working hours, but at least one of these assessments must be completed.

Scans should be performed by those with at least Royal College of Radiologists Level One accreditation (or equivalent), or by those with sufficient experience to be equivalent to this standard.

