7.1.3 Secondary endpoint analysis

Quantitative secondary endpoints will be analysed on both an intention-to-treat and, separately, a per protocol basis. Results will be presented in terms of between-group differences in either means or medians, with associated 95% confidence intervals.

Categorical data will be analysed using the Chi-squared approach (or Fisher's exact test where appropriate). Ordinal data will be analysed using the Mann Whitney U test or an independent sample t-test. Survival (time-to-event) data will be presented in the form of Kaplan-Meier curves and analysed using the Logrank test (with Cox proportional hazards analysis also performed).

The semi-structured interview component of the study will be analysed using a recognised qualitative approach, such as framework analysis, thematic analysis, or a combination of the two.

Analysis of anonymised radiological images will be performed by two clinicians, who will be blind to treatment allocation. Assessment of pleural effusion size will be performed using a recognised and previously published method. (7)

The comparison of treatment costs between randomisation and being medically fit for discharge will be performed from the perspective of the UK National Health Service, with prices of interventions or treatments being referenced from standard resources.

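### The septation outcome is a bedside score in an open-label trial, and the protocol does not assure that the planned blinded image reading covers it

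*Protocol*

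**What the plan says.** - **Outcome.** Protocol 4.3.2 lists septation among the secondary outcomes and defines it "as measured by the change in bedside thoracic ultrasound septation score from baseline to follow-up days 1, 3, 7, 30 and 90 post procedure".
- **Who scans and what is kept.** Protocol 6.5.1 states: "All thoracic ultrasound scans are to be performed as part of standard clinical care". It sets an accreditation or experience standard for the person scanning, but no requirement on blinding or independence. On capture it says: "Scan results should be documented during the baseline assessment; on the first, third and seventh days post allocated procedure", and it goes on to later time points. It does not ask for stills or clips to be saved.
- **Blinding.** Protocol 6.2.3 says that "treatment allocation will not be concealed from either participants or trial personnel".
- **Intervention.** Protocol 6.3.2 makes the breakdown of accessible septations part of the thoracoscopy.
- **Blinded reading.** Protocol 7.1.3 says: "Analysis of anonymised radiological images will be performed by two clinicians, who will be blind to treatment allocation". The next sentence is "Assessment of pleural effusion size will be performed using a recognised and previously published method". Septation is not mentioned there.
- **Image transfer.** Protocol 10.1.3 says that certain images, specified earlier in the document, will be requested and anonymised before analysis. It does not say whether ultrasound is among them.

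**The concern.** One arm receives a procedure that acts directly on the quantity being scored, and the person scoring may know who received it. If that person expects fewer septations after thoracoscopy and scores accordingly, a between-arm difference can appear without any true one.

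The protocol already has a safeguard of the right kind in the two blinded readers, but its text does not clearly extend that safeguard to septation. Nor can this be left wholly to a later analysis plan, because readers can only score images that were saved when the scan was done. Without a prospective requirement, blinded re-scoring would depend on what each site happened to keep.

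The between-arm results are meant to be used. Section 7.1.1 justifies 30 patients partly as enough to hint at possible differences between groups, and section 2.2.1 hopes the outcome data will help design and justify a larger trial.

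**Working it through.** **1. Does the text put a blinded assessor on septation?** Setting the sections side by side:

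| Question | Septation (ultrasound) | Effusion size (radiograph) |
|---|---|---|
| Outcome definition (4.3.2) | Bedside score | Radiographic hemithorax opacification |
| What is captured (6.5) | Scan results documented (6.5.1) | Images taken at listed times (6.5.2) |
| Named beside the blinded reading (7.1.3) | No | Yes |
| Blinded assessment assured by the text | No | Yes |

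No section says that the bedside scanner is unblinded. This is inferred from the open-label design (6.2.3), scanning within routine care (6.5.1), and the absence of any blinding requirement for the scanner.

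**2. Does *radiological images* in 7.1.3 include ultrasound?** The document points both ways.
- For inclusion: section 6.5, headed Imaging, contains both ultrasound and radiographs. Secondary question 4 in 3.2 treats overall complexity as something measured radiologically, and 6.2.1 assesses fluid complexity on ultrasound.
- Against inclusion: the baseline list in 6.1.2 gives the ultrasound scan and recent radiology as separate items, and 7.1.3 names only effusion size.

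The term is undefined. If ultrasound was meant, the word *bedside* in 4.3.2 conflicts with it and 6.5.1 does not secure the images needed. If it was not meant, septation has no blinded assessment. Either way the text needs an edit.

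**3. Where could an expectation effect enter?** The baseline scan is part of the baseline assessment (6.1.2), and randomisation follows that assessment (6.2.1). Baseline scores are therefore made before allocation. With change = follow-up score − baseline score, a shift in follow-up scoring passes in full into the change.

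**4. Illustration of size.** The protocol gives no scoring shift, standard deviation or significance level for this outcome, and has no figure of its own to reproduce here.
- From the documents: 30 patients allocated 1:1 (4.2), so 30 / 2 = 15 per arm. Section 7.1.3 allows a t-test for ordinal data.
- Assumed: two-sided 5% level, no true effect, all 15 per arm observed, score treated as continuous, and follow-up scores in the thoracoscopy arm lower by *d* SD of the change score.
- Degrees of freedom: 15 + 15 − 2 = 28, critical value 2.048.
- Non-centrality: *d* / √(2/15) = *d* / 0.3651.

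| Assumed shift *d* | Non-centrality | False-positive rate |
|---|---|---|
| 0 | 0 | 5.0% |
| 0.25 SD | 0.685 | 10.1% |
| 0.5 SD | 1.369 | 26.2% |

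The normal approximation gives 10.5% and 27.8% for the last two rows, so the result does not depend on the method.

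**5. Workload of a blinded reading.** Baseline plus days 1, 3, 7, 30 and 90 is 6 time points, and 30 × 6 = 180 image sets at most. Section 6.5.1 lets a day 1 or day 3 scan be omitted outside working hours, so the real number would be lower.

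**The case against.** **Silence is not a prohibition.** A reader might infer that ultrasound images are not stored, or that the blinded reading cannot be applied to septation. The protocol says neither. Sites may keep images, 10.1.3 describes local storage and anonymised transfer of certain images, and *radiological images* may have been meant to include ultrasound. The trial manual or an analysis plan could also say what the readers score. This stands, and it limits the point to blinded scoring not being assured. It does not remove the point, because the outcome is still defined as the bedside score and 6.5.1 still does not require an image.

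**Who scans.** A reader might infer that the scanner is the operator who broke down the septations. No section says so. Nor do the documents show that septation is more subjective than effusion size. The point needs neither claim.

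**The magnitude is hypothetical.** This is correct. The shifts are invented inputs, the score may be a short ordinal scale, and some scans may be missing. The percentages show how sensitive a 15-per-arm comparison would be; they do not estimate bias in this trial.

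**The consequence is small.** This also stands. Septation is one of ten secondary outcomes in a feasibility study without a power calculation, and the success criteria in 7.1.2 use only pre-screen, screen and allocation failures.

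**Blinded reading has costs.** Saving images adds a trial task to scans described as standard care, and a stored image can lose information. Using the bedside score wherever an image is missing would mix blinded and unblinded measurements in one outcome, and image availability could differ by arm or site. The fix below avoids that.

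**Conclusion.** The point holds in a limited form. As written, the protocol defines septation by a bedside score in an open-label trial, requires no blinded scanner, and does not require the images that would let the two planned readers score it. Whether their reading extends to ultrasound is ambiguous.

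Any expectation effect would act on the follow-up scores only. Its size cannot be derived from the documents. Under the stated assumptions, shifts of 0.25 SD and 0.5 SD would move a nominal 5% false-positive rate to about 10% and 26%. The primary feasibility outcome and its success thresholds are unaffected. This is a cheap improvement to one secondary outcome, worth making because it must be in place before the scans are done.

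**What to change.** 1. **Protocol 6.5.1:** require an anonymised still or clip to be saved at each scheduled trial scan.
2. **Protocol 7.1.3:** state that the two clinicians blind to allocation also score septation from these images, and define which images the blinded reading covers.
3. **Protocol 4.3.2:** make the blinded score the septation outcome. Treat a scan without a saved image as missing for that outcome.
4. **Reporting:** present the bedside score separately, as an unblinded, descriptive result, and do not use it to fill gaps in the blinded score.

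**Cost.** An image saved at scans already scheduled, and reading of at most about 180 image sets by readers already planned. Section 10.1.3 already describes an anonymised route for trial images. The main drawback is that a stored image may show less than a live scan; reporting the bedside score alongside keeps that information visible.
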